 - Inability to re-treat patient within 2 wks of scheduled treatment due to treatment-related adverse event
 - Inability to deliver all doses of Lenalidomide and or Everolimus during the first cycle due to an unexpected drug-related toxicity (if toxicity is an

expected toxicity as per current package insert, then it will not be considered a DLT). These subjects should be discontinued from the study

In the event of study discontinuation prior to completing the entire first treatment cycle for reasons other than DLT, the affected subject will be considered inevaluable for toxicity and will be replaced by another subject to be treated at the same dose-level.

Secondary:

- Significant drug-drug interaction will be determined through pharmacokinetic analysis for parent drug and metabolites (the following PK parameters will be estimated and reported for each agent according to dose level – (AUC_{0→t}) Area under the concentration-time curve from the time of dosing to the time of the last observation; (AUC_{0→∞}) Area under the concentration-time curve from the time of dosing extrapolated to infinity; (C_{max}) Maximum serum concentration observed postdose; (T_{max}) Time point at which the C_{max} occurs; (t_{1/2}) Elimination half-life, determined as 0.693/λ_z)
- The frequency of achieving a complete plus partial response to the 2 drug combination by dose cohort. Response will be assessed by cross sectional imaging after every 2 cycles and will be categorized according to RECIST 1.1 criteria.

Correlative:

- Mean change in immunological biomarkers at baseline, after 1 cycle of protocol directed therapy and at disease progression by dose cohort
- Mean change in plasma levels of inflammatory markers at baseline, after 1 completed cycle of therapy and at disease progression
- Plasma level of cathepsin G at baseline, after 1 cycle of therapy and following the first diagnosis of venous thromboembolic disease

STUDY DURATION: 18-24 months	TOTAL SAMPLE SIZE: 45

DOSING REGIMEN(S):
 
According to dose cohort:
 
Lenalidomide once daily days 1-28 of a 28 day cycle
 
Everolimus once daily continuously (day 1-28)
	
DRUG SUPPLIES:
 
For study participants, Celgene Corporation will provide lenalidomide at no charge through the RevAssist® program.
 
Everolimus will be supplied by Novartis Pharmaceuticals Corporation and dispensed through the Investigational Drug Pharmacy

2 Schedule of Study Assessments *

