10.1 Overview

All data will be listed individually by subject. Continuous variables will be summarized using descriptive statistics: mean, standard deviation, median, and minimum and maximum values. Categorical variables will be summarized using number of subjects and proportion expressed as percentage. Baseline value for any specified variable is the last valid measurement before the administration of the study drug. Unless otherwise indicated, statistical significance will be declared if the two-sided p value is ≤ 0.05 .

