10.2 Datasets to be analyzed

Demographics

Subject demographics including age, sex, race, ethnicity, height, weight, disease information, and medical conditions will be summarized by cohort using descriptive statistics.

Extent of Drug Exposure

The total number of doses of lenalidomide and everolimus (mg), and total number of treatment cycles delivered will be summarized by dose level using descriptive statistics.

Efficacy Endpoints

The secondary endpoint of the trial is response rate. The best overall response rate as defined by the proportion of subjects who have had a CR or PR will be summarized by dose level. Any subject treated in the expansion phase with overall response assessment of partial or complete response will have the response confirmed by repeat assessment no less than 4 weeks after the criteria for response are first met. The RR will be summarized by dose level using descriptive statistics along with a 95% confidence interval.

Pharmacokinetic Parameters

Serum concentration of study drug will be determined by a validated method according to assessment schedules. The pharmacokinetic parameters will be summarized using descriptive statistics.

The concentrations of everolimus, lenalidomide and their clinically significant metabolic product will be summarized by dose level using descriptive statistic. The mean concentration for each dose level will be plotted on scheduled sample time. The following pharmacokinetic parameters will be estimated and reported for each agent according to dose level.

$AUC_{0 \rightarrow t}$ Area under the concentration-time curve from the time of dosing to the time of the last observation; $AUC_{0 \rightarrow \infty}$ Area under the concentration-time curve from the time of dosing extrapolated to infinity; C_{max} Maximum serum concentration observed postdose; T_{max} Time point at which the C_{max} occurs; $t_{1/2}$ Elimination half-life, determined as $0.693/\lambda_z$.

Pharmacodynamic Correlates

The levels of mTOR pathway proteins, inflammatory cytokines and lymphocyte subsets at each specified time point will be reported in a descriptive manner for each dose schedule and analyzed by tumor type, when appropriate. Data will also be explored graphically. The PK and

pharmacodynamic data will be used to describe potential relationships between plasma levels of everolimus and or lenalidomide and changes in serum protein, toxicities, and tumor response.

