10.3 Statistical Methodology

All data will be listed individually by subject. Continuous variables will be summarized using descriptive statistics: mean, standard deviation, median, and minimum and maximum values. Categorical variables will be summarized using number of subjects and proportion expressed as percentage. Baseline value for any specified variable is the last valid measurement before the administration of the study drug. Unless otherwise indicated, statistical significance will be declared if the two-sided p value is ≤ 0.05 .

The estimation of pharmacokinetic parameters will be performed using WinNonlin® Version 5.0 or higher. All statistical analyses will be performed using SAS® Version 9.13 or higher.

Changes in immunological markers between baseline and C2D1 samples will be compared for each patient and for each dose cohort. In addition, mTOR pathway protein expression in baseline diagnostic biopsy samples will be assessed by Immunohistochemistry (IHC) and correlated with response. The dynamic changes in biomarker expression before and after one cycle of treatment with the drug combination will be summarized using summary statistics mean and standard deviation. Comparisons between the two time points will be presented graphically and subjected to statistical analysis using the Pearson's correlation coefficient.

Missing Data Handling

Unresolved missing data may be imputed when the analysis integrity is affected. The conservative principle will be used for data imputation. For example, if an adverse event onset day is missing but the adverse event onset year and month can not exclude this adverse event as a TEAE, the adverse event will be flagged as a TEAE.

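### The before-and-after-one-cycle biomarker comparison is analysed with Pearson's correlation, which cannot detect a mean shift; separately, the documents conflict on when the on-treatment blood sample is drawn

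*Combined protocol and SAP*

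**What the plan says.** **Analysis.** Section 10.3 takes three steps on biomarkers.
- For blood: "Changes in immunological markers between baseline and C2D1 samples will be compared for each patient and for each dose cohort". No method is named.
- Baseline tissue expression is to be correlated with response, which is a separate question.
- The "dynamic changes in biomarker expression before and after one cycle of treatment with the drug combination will be summarized" by mean and standard deviation, followed by: "Comparisons between the two time points will be presented graphically and subjected to statistical analysis using the Pearson's correlation coefficient".

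No other test of two time points appears in the documents. Section 10.1 sets the default rule that "statistical significance will be declared if the two-sided p value is" 0.05 or less. Section 10.2 adds that marker levels at each time point "will be reported in a descriptive manner for each dose schedule" and explored graphically.

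**Endpoints.** The synopsis lists "Mean change in immunological biomarkers at baseline, after 1 cycle of protocol directed therapy and at disease progression by dose cohort" and "Mean change in plasma levels of inflammatory markers at baseline, after 1 completed cycle of therapy and at disease progression". It treats cathepsin G on its own: "Plasma level of cathepsin G at baseline, after 1 cycle of therapy and following the first diagnosis of venous thromboembolic disease".

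**Samples.** Section 4.2.3 allows paired fresh biopsies in up to 15 patients. Footnote 13 of the schedule sets them at baseline and the end of cycle 1, optional and in the expansion cohort only. Section 5.1.3 makes them depend on experience in escalation and on the supporter's approval. The timing statements for blood are set side by side in the working.

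**The concern.** The stated interest is whether treatment moves the markers. The only inferential method named for the two time points measures linear association between baseline and on-treatment values. A significant result would mean that patients who start high tend to stay high. It could appear when nothing changed and be absent when every patient changed. Under the plan's 0.05 rule, such a result could be reported as pharmacodynamic evidence of target modulation, which is the correlative objective in section 4.1.3.

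The blood contrast has a second, independent problem. Its planned on-treatment time point is day 1 of cycle 2, but the collection instructions name different days. A patient sampled strictly under Appendix D would have no sample for that contrast, and a later sample could be reported as if taken after one cycle.

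**Working it through.** **Inputs from the documents.** Two-sided 0.05 (10.1, 10.3); at most 15 tissue pairs (4.2.3); up to 6 patients per dose level (10.6); 28-day cycles. The plan gives no size or power figure for the biomarker comparison, so there is none to reproduce.

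**Assumptions, not in the documents.** Bivariate normal values, equal SDs before and after, within-patient correlation ρ of 0, 0.5 or 0.8, and a true shift of 0 or 1 SD.

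**Step 1: algebra.** r = Σ(xᵢ − x̄)(yᵢ − ȳ) / √[Σ(xᵢ − x̄)² Σ(yᵢ − ȳ)²]. Adding c to every yᵢ adds c to ȳ, so each deviation, r and its p value stay the same. This needs no distributional assumption.

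**Step 2: one simulated set of 15 pairs.**

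| Constant added | Mean difference | Pearson r (p) | Paired t p |
|---|---|---|---|
| 0 | −0.44 | 0.5589 (0.0303) | 0.30 |
| 1 | 0.56 | 0.5589 (0.0303) | 0.20 |
| 5 | 4.56 | 0.5589 (0.0303) | 2.6 × 10⁻⁸ |
| 50 | 49.56 | 0.5589 (0.0303) | 1.7 × 10⁻²² |

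**Step 3: how often each test is significant** (40,000 simulated trials per setting; entries for ρ = 0 / 0.5 / 0.8). Pearson uses t = r√[(n − 2)/(1 − r²)] on n − 2 degrees of freedom.

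| n | Pearson, shift 0 | Pearson, shift 1 SD | Signed-rank, shift 0 | Signed-rank, shift 1 SD |
|---|---|---|---|---|
| 15 | 5% / 50% / 98% | 5% / 50% / 98% | 5% / 5% / 5% | 70% / 94% / >99% |
| 8 | 5% / 25% / 75% | 5% / 25% / 75% | 4% / 4% / 4% | 35% / 61% / 94% |

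At n = 15 and a 1 SD shift the paired t-test gives 72% / 95% / >99%, which agrees with the noncentral t distribution. If the sentence also covers blood markers by dose cohort, Pearson at n = 6 gives about 5% / 17% / 55% with either shift.

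**Step 4: what an interval would show.** The 95% half-width for mean change, in SD units, is t(0.975, n − 1) × √[2(1 − ρ)/n].
- n = 15, ρ = 0.5: 2.145 × √(1/15) = 0.55. For ρ = 0 and 0.8 it is 0.78 and 0.35.
- n = 8: 1.18 / 0.84 / 0.53.
- n = 3: 3.5 / 2.5 / 1.6.

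**Step 5: blood timing, side by side.**

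| Source | On-treatment draw (besides progression) |
|---|---|
| Synopsis, correlative endpoints | after 1 cycle |
| 4.2.3 | end of cycle 1 |
| 10.3 | C2D1 |
| Schedule, footnote 11 | first two restagings; names C3D1 ± 2 days |
| 5.1.4, 5.1.5 | first two restagings |
| Appendix D | C3D1 and C5D1, each ± 2 days |

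Without delays, C2D1 is day 28 + 1 = 29 and C3D1 is day 56 + 1 = 57, so ± 2 days spans days 55 to 59. Neither that window nor the general ± 3 days bridges the 28-day gap.

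The schedule grid does not settle it. The on-treatment blood mark sits under day 1 of cycles 2, 4, 6, 8, carries footnote 11 and shares that column with the restaging scans. Yet the biopsy mark, defined as end of cycle 1, is in the same column, and the blood cell under cycles 3, 5, 7, 9 is blank.

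**The case against.** **Change is already described.** Mean, SD, graphs and individual listings are planned, and a phase I correlative endpoint needs no significance test. This stands: a reader might infer that change goes unanalysed, and the documents do not support that. Deleting the Pearson analysis and staying descriptive would be defensible. But the plan does choose a test, applies a 0.05 rule, and plans no interval for the change.

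**The reach is narrow.** The sentence clearly covers only paired tissue, which may not be collected at all. This also stands. If blood is outside it, however, the baseline-to-C2D1 comparison has no stated method.

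**Timing.** A reader might infer that blood is simply scheduled at restaging, or that the escalation patients have no C2D1 sample. The documents do not support either. Section 4.2.3 and the synopsis are current text and place a draw after cycle 1, the grid lends that some support, and nothing says which schedule the 21 escalation patients followed. Nor does the conflict extend to biopsies, whose timing is consistent, or clearly to cathepsin G: footnote 11 does not name it and Appendix D gives no collection instruction for it.

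**False positives.** A reader might take the 50% and 98% as inflated type I error. They are not: with ρ above 0 the test correctly rejects zero correlation. The fault is the question asked. Counting false positives across the marker panel would describe a valid test of change, not this defect.

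**Conclusion.** The Pearson analysis is wrong as written for its stated purpose. That conclusion rests on algebra alone. The percentages rest on the assumed normality, equal SDs and correlations, and 15 pairs is a ceiling. Under them, Pearson at n = 15 gives the same 5% / 50% / 98% with no shift as with a 1 SD shift, so it carries no information on change. Change would still be described, but not validly tested.

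The blood-timing conflict is a separate defect: three places point to the end of cycle 1, and four point to restaging about 28 days later. It is a contradiction to reconcile, not proof that a sample is missing. Both matters concern correlative endpoints and should be corrected; the MTD is unaffected.

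**What to change.** **Analysis (SAP wording only).**
- Delete Pearson's correlation as the analysis of the two time points. Report within-patient change with a 95% interval for each marker.
- Add at most one exploratory paired test, matched to the interval: mean change with a t interval and paired t-test on a suitable scale, or the Hodges-Lehmann estimate and interval with the exact signed-rank test, with a rule for ties and zeros because immunoscores may tie. Mixing a t interval with a signed-rank p value invites contradiction: at n = 6, ρ = 0.5 and a 1 SD shift, the two disagree in about 18% of simulated trials.
- In cohorts of 3 to 5, give the estimate and interval only. The smallest two-sided signed-rank p is 2/2ⁿ, that is 0.25, 0.125 and 0.0625. For the same reason no exact 95% signed-rank interval exists there, so a t interval would be needed.
- Label p values exploratory and unadjusted, and state whether blood markers are covered.

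The choice of test costs little at n = 15 (signed-rank 70% against paired t 72% at ρ = 0, 1 SD shift) but more at n = 6 (36% against 51% at ρ = 0.5).

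**Blood timing (protocol correction).** State one on-treatment contrast identically in the synopsis, grid, footnote 11, 4.2.3, 5.1.4, 5.1.5, 10.3 and Appendix D, and give cathepsin G its own line. Analyse samples already drawn under the time point actually collected, and do not pool C3D1 draws as after one cycle. If C2D1 is kept, later patients may need one added draw; past draws cannot be changed.

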10.4 Safety evaluation

Data from all subjects who receive any protocol therapy will be included in the safety analyses. Subjects who entered the study and did not receive any protocol therapy and had this confirmed, will not be evaluated for safety.

The severity of the toxicities will be graded according to the NCI CTCAE v4.0 whenever possible. The safety analysis will be conducted on all enrolled patient population. The following safety parameters will be evaluated:

Adverse Events

A treatment-related adverse event (TRAE) is defined as a sign or symptom that emerges during treatment or within 30 days after the last dose of study drug, having been absent pre-treatment or that has worsened relative to the pretreatment state. Any adverse events deemed related to study drug will also be considered a TRAE regardless of the elapsed time since the last dose of study drug. Adverse events will be coded using the Medical Dictionary for Regulatory Activities (MedDRA) to categorize the event to a system organ class and a preferred term. The number of subjects who experienced at least 1 adverse event, severe (\geq Grade 3) adverse event, study drug-

related adverse event, serious adverse event, and the number of subjects discontinued due to adverse events will be summarized by dose level. For each system organ class and preferred term, summaries will be made with respect to the number and proportion of subjects having at least 1 occurrence of an adverse event during the study. The incidence of adverse events will be presented overall, by system organ class and preferred term, intensity (based on CTCAE Version 4.0), TRAEs, and additional grouping by severity and relationship to study drug. An individual listing of adverse events will be provided. DLTs and study drug-related \geq Grade 2 adverse events will be listed individually.

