6.3 Adverse events – RAD001

Information about all adverse events, whether volunteered by the subject, discovered by investigator questioning, or detected through physical examination, laboratory test or other means, will be collected and recorded and followed as appropriate.

An adverse event is the appearance or worsening of any undesirable sign, symptom, or medical condition occurring after starting the study drug even if the event is not considered to be related to study drug. Medical conditions/diseases present before starting study drug are only considered adverse events if they worsen after starting study drug. Abnormal laboratory values or test results constitute adverse events only if they induce clinical signs or symptoms, are considered clinically significant, or require therapy.

The occurrence of adverse events should be sought by non-directive questioning of the patient at each visit during the study. Adverse events also may be detected when they are volunteered by the patient during or between visits or through physical examination, laboratory test, or other assessments. As far as possible, each adverse event should be evaluated to determine:

1. the severity grade (mild, moderate, severe) or (grade 1-4)

-
2. its relationship to the study drug(s) (suspected/not suspected)
 3. its duration (start and end dates or if continuing at final exam)
 4. action taken (no action taken; study drug dosage adjusted/temporarily interrupted; study drug permanently discontinued due to this adverse event; concomitant medication taken; non-drug therapy given; hospitalization/prolonged hospitalization)
 5. whether it constitutes a serious adverse event (SAE)

All adverse events should be treated appropriately. Such treatment may include changes in study drug treatment including possible interruption or discontinuation, starting or stopping concomitant treatments, changes in the frequency or nature of assessments, hospitalization, or any other medically required intervention. Once an adverse event is detected, it should be followed until its resolution, and assessment should be made at each visit (or more frequently, if necessary) of any changes in severity, the suspected relationship to the study drug, the interventions required to treat it, and the outcome.

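### Section 10.4 gives the name treatment-related to a treatment-emergent definition, so the TRAE output would include events the investigator judged unrelated

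*Combined protocol and SAP*

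**What the plan says.** The adverse event text of section 10.4 defines the category: "A treatment-related adverse event (TRAE) is defined as a sign or symptom that emerges during treatment or within 30 days after the last dose". It adds the baseline condition "having been absent pre-treatment or that has worsened relative to the pretreatment state". Relatedness appears only in the next sentence: "Any adverse events deemed related to study drug will also be considered a TRAE regardless of the elapsed time since the last dose".

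The same section then plans several outputs. Incidence is to be presented overall, by MedDRA term, by intensity, and by "TRAEs, and additional grouping by severity and relationship to study drug". Separately, a by-dose-level summary counts subjects with a study drug-related event. The sentence breaks across a page and resumes with the end of that term: "related adverse event, serious adverse event, and the number of subjects discontinued due to adverse events will be summarized by dose level". DLTs and drug-related events of Grade 2 or higher are to be listed individually.

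In section 10.3, the missing-data rule says that if an incomplete onset date cannot rule out emergence, "the adverse event will be flagged as a TEAE". The documents do not define TEAE.

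Causality is recorded. For everolimus, section 6.3 asks that each event be assessed for "its relationship to the study drug(s) (suspected/not suspected". Section 6.2 requires a relationship judgement in the lenalidomide reporting text.

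**The concern.** The label states a causal judgement that the definition does not require. Assessing safety and tolerability is a primary objective (section 4.1.1). The study is non-randomized (section 5.1), so no concurrent control shows the background rate of events in patients with advanced cancer. In that setting, readers look to the relatedness label to separate the regimen's effects from the disease and intercurrent illness.

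Under the definition as written, a symptom of progression that starts on treatment is a TRAE even if the investigator attributes it to the cancer. The report would then carry two categories, treatment-related and study drug-related, that mean the same in words but hold different events. Nothing in the plan says which one answers the tolerability question.

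**Working it through.** There is no stated figure to reproduce and no arithmetic to run on the plan's own numbers. The check is a logical reading of the definition against the other sections.

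**Step 1. The rule in section 10.4.** Let E = new or worsened on treatment or within 30 days of the last dose, and R = judged related to study drug. The first sentence makes E sufficient. The second adds R at any time, and its word *also* shows that R is an extra route and not a further condition. So:

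- TRAE as written = E or R
- Study drug-related = R

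**Step 2. Apply both rules to each kind of event.**

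| Event | Causality | TRAE as written | Study drug-related |
|---|---|---|---|
| New or worsened, in window | Suspected | Yes | Yes |
| New or worsened, in window | Not suspected | **Yes** | **No** |
| After the window | Suspected | Yes | Yes |
| After the window | Not suspected | No | No |

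The two categories differ in one row. Every drug-related event is a TRAE, so the TRAE count can never be the lower of the two:

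- TRAE events − drug-related events = in-window new or worsened events judged not suspected
- For a given term, TRAE subjects − drug-related subjects = subjects with at least one such event and no related event under that term

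**Step 3. Compare with the document's own vocabulary.** Section 3.5 (everolimus part) reports treatment-emergent events in a cited trial and says that they are counted irrespective of causality. The protocol therefore already separates emergence from relatedness. Section 10.3 uses TEAE for a timing rule, which is the concept that section 10.4 defines under the name TRAE. The likeliest explanation is that *related* was written where *emergent* was meant.

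**Step 4. Follow the undefined term.** If a programmer takes TEAE in section 10.3 to mean the section 10.4 category, an event with an incomplete onset date could be reported as treatment-related through the date rule alone. That rule is conservative for emergence, but it says nothing about cause.

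**Step 5. Check whether the label reaches dose decisions.** Section 4.2.1 lists the DLT criteria, and Table 1 in section 5.1 gives the escalation rules. Neither cites the TRAE category or section 10.4.

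**Step 6. Check the causality scale.** Section 6.3 uses two levels, suspected or not. Section 6.4 gives three examples: probable, unknown and definitely not related. A corrected definition has to say which scale applies and where an unknown relationship falls.

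**The case against.** The strongest reply is that this is a slip of terminology with little consequence. TRAE appears once among the planned outputs. Section 10.4 also plans drug-related counts by dose level, a grouping by relationship, an individual listing of adverse events, and a listing of drug-related events of Grade 2 or higher. Section 6.3 already defines an adverse event as one appearing or worsening after study drug starts, related or not, so the overall tables are close to treatment-emergent. Attribution is not lost.

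Most of this stands, and it limits the point to outputs labelled TRAE. It does not remove the error. Section 10.4 is the operative definition: a programmer who follows it produces a mislabelled table, and one who silently corrects it departs from the plan.

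Three stronger readings are tempting, and the documents do not support them.

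- **That the report as a whole would present every new event as drug-related and overstate the regimen's toxicity.** The separately planned drug-related outputs rule this out.
- **That the size can be read from the placebo-controlled everolimus trial in section 3.5.** There, events led to discontinuation in 14% on drug and 3% on placebo, and 3/14 = 21%. That ratio divides per-patient discontinuation rates from a single-agent trial, and it is not the share of events mislabelled here. Median exposure also differed, at 141 against 60 days. Crude scaling gives 3% × 141/60 = 7.05%, and 7.05/14 = 50%, so the ratio is not even stable. Subtracting a placebo rate is also not investigator attribution.
- **That dose escalation is affected.** One DLT criterion in the synopsis, on delayed re-treatment, uses the words treatment-related adverse event. Section 4.2.1 words the same criterion as toxicity, and neither place refers to section 10.4.

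**Conclusion.** The definition is wrong as written and should be corrected before the safety tables are programmed. It names as treatment-related a category that includes every new or worsened event on treatment or within 30 days of the last dose, whatever the investigator's judgement. The TRAE presentation would equal or exceed the drug-related one, with the excess made up of in-window events judged not suspected.

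The size of that excess depends on how many such events occur, and the documents give no figure from which to estimate it. The consequence is two conflicting related categories in the safety report and an undefined TEAE in section 10.3. It does not extend to the MTD, the DLT rules or the drug-related summaries. The conclusion assumes that section 10.4 is programmed literally and that causality is recorded for each event as sections 6.2 and 6.3 require.

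**What to change.** 1. In section 10.4, rename the present timing-and-worsening definition *treatment-emergent adverse event (TEAE)*. This also supplies the definition missing from section 10.3.
2. Move the sentence on later related events out of that definition. Define TRAE as a TEAE, or a later event, that the investigator judges related to lenalidomide, everolimus or both.
3. Name one causality scale. Reconcile sections 6.3 and 6.4, and state whether an unknown relationship counts as related.
4. State that TRAE and study drug-related are the same category, and use one term throughout.
5. Mark each planned summary and listing in section 10.4 as based on TEAEs or on TRAEs.

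The cost is a few sentences of analysis text. Causality is already collected and drug-related summaries by dose level are already planned, so no new data or additional set of tables is needed. Patient management does not change.
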